5.7.2. Analysis Model

The linear mixed effects model for TBUT can be written as follows:

$$y_{ij} = \beta_0 + \beta_1 T_i + \beta_2 TBUT_{ij,0} + b_{0i} + \epsilon_{ij}$$

Where

- $TBUT_{ij,k}$ is the TBUT value for subject i, eye j, week k.
- y_{ij} is the 1 month change from baseline TBUT for subject i, eye j. $y_{ij} = TBUT_{ij,4} - TBUT_{ij,0}$
- T_i is the binary treatment indicator for subject i (0 = Control, 1 = IPL Laser)
- $\beta_0, \beta_1, and \beta_2$ are the fixed effect parameters:
 - \circ β_0 is the mean change from baseline for the Control arm,
 - β_1 is the difference between IPL and Control in mean change from baseline,
 - \circ β_2 is the effect of each unit change in baseline TBUT.

- b_{0i} is the random effect (random intercept term) for subject i $b_{0i} \sim N(0, \sigma_a^2)$
- ϵ_{ii} is the normally-distributed error term ٠ $\epsilon_{ij} \sim N(0, \sigma_e^2)$
- $\{b_{0i}\}$ and $\{\epsilon_{ii}\}$ are independent

The linear mixed effects models can be fit in SAS or R as follows:

In SAS:

Proc Mixed data=IPLdat method=ml; class SUBJ TRT; model TBUT_DIFF = TRT TBUT_BL / solution; random intercept / subject=SUBJ;

In R:

Library(Ime4) fit.tbut <- Imer(TBUT.DIFF ~ TRT + TBUT.BL + (1|SUBJ), REML=FALSE, data=IPLdat)

Note that since we are interested in testing the fixed effects, ML (maximum likelihood) versus REML (residual maximum likelihood) estimates are being used.

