	6. Self-assessment of pain/discomfort during IPL administration, using a VAS			
	7. Self-assessment of pain/discomfort during MGX, using a VAS			
	There will be a single follow-up (FU) visit, which will occur 4 weeks (-3 days, + 7 days) after the final treatment session. Subjects will undergo the following assessments, in the specified order:			
	 Subject's report of the daily usage (frequency and dose) of eye drop, warm compresses and lid hygiene since the previous visit 			
	2. Three consecutive measurements of TBUT in both eyes			
Follow-up (FU)	3. Routine ophthalmology tests in both eyes, including: biomicroscopy, BCVA and IOP			
visit	4. OSDI, self-assessed using an OSDI questionnaire			
	5. EDS, self-assessed using a VAS			
	6. High resolution close-up photos of both eyes, including: iris, lid margins and eyelashes			
	7. Meibography of the upper and lower eyelids in both eyes			
	8. Meibomian gland secretion (MGS) score in 15 glands of the lower eyelid in both eyes			
Safety outcome measures	 incidence of non-ocular adverse events throughout the study incidence of ocular adverse events throughout the study incidence of unanticipated serious adverse events throughout the study self-assessment of pain/discomfort of IPL in treatment sessions (using a VAS) self-assessment of pain/discomfort of MGX in treatment sessions (using a VAS) 			
Covariates	Baseline TBUT (continuous)Baseline skin rosacea (4-point scale)			
	The following assumptions were used to calculate the original sample size:			
Sample Size	(1) In the study arm, the change of TBUT from BL to FU \approx 5 \pm 5 sec (2) In the control arm, the change of TBUT from BL to FU \approx 1 \pm 5 sec			

	(3) A type I error of 0.05 (two-tailed test)				
	(4) A type II error of 0.2 (power = 0.8)				
	(5) A 1:1 ratio of Treatment to Control				
	With these assumptions, the minimal sample size was calculated to be 50 evaluable subjects (100 evaluable eyes): 25 subjects (50 eyes) in the control arm and 25 subjects (50 eyes) in the study arm.				
	Assuming a dropout rate of 15%, the anticipated number of enrolled subjects was 59. Assuming a screening failure rate of 15%, the anticipated total number of screened subjects was 69.				

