2.2. Success criterion

The study will be determined as successful if it satisfies two conditions:

- 1. The difference in the change of TBUT, between eyes in the study arm and eyes in the control arm, is statistically significant at the α = 0.05 level.
- 2. The *change* of TBUT is *higher* in eyes of the study arm, compared to eyes of the control arm

where the *change* of TBUT is defined as TBUT at the follow-up minus TBUT at the baseline.

- **2.3.** Secondary efficiency endpoints
 - The difference in the *change* of OSDI, between subjects in the study arm and subjects in the control arm
 - The difference in the *change* of EDS, between subjects in the study arm and subjects in the control arm

where the *change* of the variable (OSDI or EDS) is defined as the value of the variable at the follow-up minus the value of the variable at the baseline.

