4.1. Effectiveness

4.1.1. Primary effectiveness endpoint

The primary efficiency endpoint will be estimated as the difference in the *change* of TBUT from baseline to follow-up (10 weeks) between the study arm and the control arm, where the change of TBUT is defined as TBUT at the follow-up minus TBUT at the baseline.

A linear mixed-effect (LME) model will be used to test the null hypothesis that the changes of TBUT are not different between the two arms. The success criterion will include the following two conditions:

- 1. Two-sided p-value < 0.05
- 2. The change of TBUT in eyes of the study arm is *larger* than the change of TBUT in eyes of the control arm

The linear mixed-effect model will include a random effect for subjects to account for correlation between eyes within subjects.

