5.7. Effectiveness analyses

The primary efficacy outcome measure (TBUT) consist of a pre-treatment measurement (the baseline), a treatment intervention, and a post-treatment measurement (the follow-up). Both eyes will be included in the analysis. Since the two eyes of a subject are not independent, to estimate whether TBUT has improved from the baseline to the follow-up, a linear mixed effects model with random intercept, using the subject identity as the random effect, is the appropriate test. Since there are two eyes per person then there is only one possible covariance structure (i.e. symmetric, with a single correlation between eyes).

The secondary efficacy outcome measures are OSDI and EDS which will be collected at the baseline, and at a follow-up visit. In the case of OSDI, the value is estimated per subject. Hence, a single value will be collected per subject at each of these two visits. In this case a paired t-test is the appropriate statistical test to estimate whether dry eye symptoms have improved, using the change of OSDI from baseline to the follow-up. In the case of EDS, the value is estimated per eye. Hence, two values will be collected per subject at each of these two visits. Since the two eyes of a subject are not independent, to estimate whether EDS has improved from the baseline to the follow-up, a linear mixed effects model with random intercept, using the subject identity as the random effect, is the appropriate test. The level of

statistical significance is $\alpha = 0.05$. Non-parametric tests will be performed if the underlying distributions are not normal.

For all other eye-level analyses, where appropriate, sample means of continuous variables will be analyzed with linear mixed effects model with random intercept (whenever both eyes of a subject are included in the analysis), or two-sample t-tests. Proportions will be analyzed with χ^2 tests.

All statistical tests will be two-sided because potentially the treatment procedure may worsen the outcome. The level of statistical significance (type I error) is $\alpha = 0.05$. Non-parametric tests will be performed if the underlying distribution is not normal.

For descriptive statistics, the N, Mean, Median, Standard deviation, Standard error of the mean, 95% confidence interval, Minimum, and Maximum will be reported for continuous variables; the frequency and proportion for each category will be reported for nominal and categorical variables.

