A previous study demonstrated that in subjects with a lower TBUT at the baseline, the change in TBUT at the follow-up was larger [21]. Although not shown in this study, the severity level of skin rosacea at the baseline may also be a confounder. Hence, in addition to the primary analysis, we will carry out an analysis of covariance (ANCOVA) to adjust for these covariates.

The following baseline covariates will be included in the ANCOVA:

- (1) TBUT at baseline. This covariate will be treated as continuous.
- (2) The 4-point severity level of skin rosacea at baseline (0= none; 1 = mild; 2 = moderate; 3 = severe). This covariate will be treated as either a numeric score (continuous) or using orthogonal polynomial contrasts.

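### The plan describes a primary TBUT model with no named covariate but writes and codes one adjusted for baseline TBUT, and never says which fit decides success

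*SAP*

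**What the plan says.** Success needs a two-sided p-value below 0.05 and a larger TBUT change "in eyes of the study arm, compared to eyes of the control arm" (SAP 2.2; also SAP 4.1.1 and Protocol 6.1.1). On the model behind that p-value, the documents say the following.

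- SAP 4.1.1: "The linear mixed-effect model will include a random effect for subjects to account for correlation between eyes within subjects". No covariate is named.
- SAP 5.7, and Protocol 7.4 in the same words: for TBUT, "a linear mixed effects model with random intercept, using the subject identity as the random effect, is the appropriate test". Again no covariate is named.
- SAP 5.7 and Protocol 7.4, on baseline TBUT and 4-point rosacea severity: "Hence, in addition to the primary analysis, we will carry out an analysis of covariance (ANCOVA) to adjust for these covariates".
- SAP 5.7.2: "The linear mixed effects model for TBUT can be written as follows". The equation, the SAS code ("Proc Mixed data=IPLdat method=ml; class SUBJ TRT; model TBUT_DIFF = TRT TBUT_BL / solution; random intercept / subject=SUBJ") and the R code all contain treatment, baseline TBUT and a random subject intercept. Rosacea appears in none of them.
- Both synopses list baseline TBUT and rosacea as covariates without tying them to an analysis.

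**The concern.** The text puts covariate adjustment beside the primary analysis; the code puts half of that adjustment inside the only TBUT mixed model that is written out. A statistician who runs the printed code does not run the analysis that SAP 5.7 describes, and one who follows SAP 5.7 does not run the printed code.

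The success criterion rests on a single p-value. With two documented candidates and no rule between them, a result in which the fits fall on opposite sides of 0.05 would be open to dispute, whichever was reported. It would also be hard to show that the choice did not depend on the data.

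**Working it through.** **1. The passages side by side**

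| Place | Baseline TBUT | Rosacea | Status given |
|---|---|---|---|
| SAP 4.1.1, Protocol 6.1.1 | not named | not named | carries the success criterion |
| SAP 5.7, Protocol 7.4 (mixed model) | not named | not named | test for the primary outcome |
| SAP 5.7, Protocol 7.4 (ANCOVA) | included | included | additional to the primary |
| SAP 5.7.2 (equation and code) | included | omitted | none stated |

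The 5.7.2 model matches neither the covariate-free description nor the two-covariate ANCOVA. It is also inconsistent within itself: it says of the intercept that it "is the mean change from baseline for the Control arm". With an uncentred covariate that does not hold in general; it describes the unadjusted model.

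**2. The plan's own sample sizes**

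Original size: n per arm = 2 × (1.960 + 0.842)² × 5² / 4² = 24.5, rounded up to 25, so 50 in total, as stated. Adjusted size: with 68 subjects and 8 of 34 IPL subjects responding like controls, the difference is 4 × 26/34 = 3.06 s. The SD of a two-eye mean is 5 × √((1 + 0.5)/2) = 4.33 s. Two-sided t-test power is 0.82, consistent with the intended 0.80. Neither calculation uses a covariate, and neither changes if one model is named.

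**3. How often the two models disagree**

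Inputs from SAP 5.3.2: 83 subjects (taken as 42 IPL and 41 control), SD 5 s, between-eye correlation 0.5, planned difference 4 s, 8 IPL subjects with no effect. Assumptions not in the documents: the correlation r between baseline TBUT and its change (SAP 5.7 supports a negative sign, not a size), a between-eye correlation of 0.5 for baseline, and a smaller true effect of 2.5 s as a further case.

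Each simulated trial was fitted by REML with and without baseline TBUT, using t tests on 81 and 80 df. There were 30,000 trials per cell with dilution, 20,000 at 2.5 s and 60,000 under the null. Success means p < 0.05 with IPL better.

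| r | Power, unadjusted (diluted) | Power, adjusted (diluted) | Opposite verdicts (diluted) | Opposite verdicts (2.5 s) | Null: either fit succeeds |
|---|---|---|---|---|---|
| 0 | 0.910 | 0.909 | 0.9% | 1.6% | 2.7% |
| -0.1 | 0.909 | 0.911 | 1.4% | 2.8% | 2.8% |
| -0.2 | 0.909 | 0.918 | 2.7% | 5.3% | 3.0% |
| -0.3 | 0.911 | 0.934 | 4.0% | 8.1% | 3.2% |
| -0.4 | 0.911 | 0.949 | 5.1% | 11.7% | 3.5% |

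Under the null, each model alone succeeds in 2.5-2.7% of trials. With a baseline between-eye correlation of 0.7 instead, and the dilution entered as a uniform 3.23 s difference (1,500 trials per cell), opposite verdicts occur in 1.1%, 2.3% and 4.2% at r = 0, -0.2 and -0.4.

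**4. If the mistreated subjects are excluded**

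The diluted case follows the ITT assumption in SAP 5.3.2. SAP 3.3 instead puts the primary analysis on a per-protocol population without major deviations. If the 8 IPL subjects are dropped (34 against 41, 4 s), opposite verdicts occur in about 0.5-0.6% of trials at r = 0, 1.4% at -0.3 and 1.8-2.0% at -0.4. Sham subjects at that site were also treated off-instruction, but their number is not given, so they are kept in this case.

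**5. Why r stops at -0.4**

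The slope of change on baseline is r × 5 / (baseline SD). With an assumed baseline SD of 2 s, r = -0.4 gives -1.0, so follow-up TBUT is unrelated to baseline. At r = -0.5 the slope is -1.25, and follow-up would fall by 0.25 s for each extra second of baseline TBUT, which is not a credible bound.

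**6. Minor points in SAP 5.7.2**

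With an assumed baseline mean of 4 s and SD of 2 s, r = -0.3 gives a slope of -0.75. The intercept is then 1 + 0.75 × 4 = 4.0 s, against a planned control change of 1 s. The treatment test is unaffected. ML makes the standard error about 1.5% too small (ratio to REML 0.985), giving a two-sided type I error of 5.3-5.5% with t and 5.6-5.9% with z. No test or df method is named.

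**The case against.** The descriptions in SAP 4.1.1 and 5.7 name a class of model and never call it unadjusted. SAP 5.7.2 sits under the effectiveness analyses and holds the only equation and code, so it could be the model that 4.1.1 means, with the ANCOVA adding rosacea. Equally, 5.7.2 never calls its model primary and is worded permissively, so the code could be illustrative. Both readings are available, which is why the passages count as unreconciled. The first has to explain why SAP 5.7 lists baseline TBUT among the additional adjustments; the second, why the only printed code differs from the primary analysis.

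It is also fair that deleting the covariate from 5.7.2, or labelling that code supportive, would reconcile the texts without touching the protocol. Adopting the adjusted model is a preference, though one that rests on the sponsor's own rationale and code.

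A reader might infer more than the documents support: that the primary is settled as unadjusted and the code is simply a mistake, that baseline adjustment is improper, or that the sponsor will choose the fit after unmasking. Nothing establishes the first. The second is wrong, since each model holds its error rate. The third is a possibility left open, not something the documents show.

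**Conclusion.** The conflict holds on the text with high confidence: two candidate primary models and no sentence choosing between them. Its numerical consequence is modest and less certain, because it rests on an assumed r of 0 to -0.4. Opposite verdicts would occur in about 1-5% of trials with the 8 subjects kept, about 0.5-2% with them excluded, and 1.6-11.7% if the true effect were an assumed 2.5 s. The false-success figure of at most about 3.5% applies only if the better of the two fits were always taken; it is not the error rate of either model. This should be corrected, but it does not invalidate the design or the sample size.

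**What to change.** Before unmasking, name one primary model: TBUT change on treatment and baseline TBUT with a random subject intercept. State it in SAP 4.1.1, 5.7, 5.7.2 and the SAP synopsis. Align Protocol 7.4 and the protocol synopsis by amendment, or record the change as a documented SAP deviation; otherwise the protocol still contradicts the SAP. Label the unadjusted and rosacea-adjusted fits as sensitivity analyses. Leave the stratified analysis in SAP 5.7.1 and its decision rule unchanged here, since it raises separate questions.

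The cost is wording in both documents and one degree of freedom. No new data are needed, because baseline TBUT is already measured in both eyes. In the diluted case, power is 0.91 with either model at r = 0; with adjustment it rises to about 0.93 at r = -0.3 and 0.95 at r = -0.4.

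Two minor edits can go in at the same time: centre baseline TBUT or correct the intercept definition, and fit by REML with a stated df method (for example Kenward-Roger).

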5.3.1. Original calculation of the sample size

Assuming a 1:1 randomization ratio, a mean of 5 ± 5 sec for \triangle TBUT of the study arm, a mean of 1 ± 5 sec for \triangle TBUT of the control arm, an alpha level of 0.05 and a power of 80%, the total sample size is 50 completed study eyes (25 for the study arm and 25 for the control arm). Assuming a dropout rate of 15%, the anticipated number of enrolled subjects is 58. Assuming a screening failure rate of 15%, the anticipated total number of screened subjects is 66.

In addition, MGD is less common without concomitant skin rosacea. Therefore, enrollment will continue until at least 10 subjects without skin rosacea are enrolled, even if 58 subjects were already enrolled.

5.3.2. Adjusted calculation of the sample size.

After the corrective action to remedy the treatment errors, the sample size was recalculated using a simulation where we made the following conservative assumptions:

- The initial 8 IPL subjects at the affected site had response equal to the control arm (1±5 seconds)
- Subsequent to the corrective action, IPL subjects at the affected site had a response equal to the IPL arm (5±5 seconds)
- The final analysis was ITT, which included the inappropriately treated patients in the IPL arm.
- The correlation between eyes within a subject is 0.5.

Under these assumptions the overall treatment effect is "diluted" by the initial set of patients who were treated inappropriately. Under these conservative assumptions, the sample size needed to restore the original power was calculated to be 136 evaluable eyes (68 subjects, i.e. 18 subjects more than the original 50 subjects).

In addition, in order to allow for full comparison of the effect of the corrective action, 15 patients were added to the enrollment at the affected site so there would be sufficient before/after patients to allow for clinical evaluation of the difference.

Adding these 33 (18+15) subjects to the original 50 completed subjects, the number of completed subjects is up to 83. Therefore, with a loss to follow-up rate of 7% the expected number of enrolled subjects is 89, and with a screening failure rate of 23% the expected number of screened subjects is 116.

All sample size re-calculations were done prior to any unmasking of any results from the study.

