5.7.1. Stratified Analysis

To account for the potential loss of IPL treatment effect at one site (hereafter called "A") a stratified analysis will be performed that includes a separate stratum comprising subjects at site A who were treated prior to the corrective action. The strata will be labeled as A1, A2, B, and C for sites A, B, and C, with A1 and A2 the two separate groups of patients at site A before and after the corrective action. Since the treatment is applied over a sequence of four visits, we will conservatively assign to stratum A2 only those patients who received all four of their treatments subsequent to the corrective action. Any patient who received any one of their four scheduled treatments prior to the corrective action will be assigned to stratum A1.

Stratum	Corrective Action	Description
A1	No	Patients from site A with one or more treatment visits prior to the corrective action

Thus, the following four strata are obtained:

A2	Yes	Patients from site A with all 4 treatment visits subsequent to the corrective action
В	No	Patients from site B
C	No	Patients from site C

An ANOVA analysis will be performed for the change in TBUT primary endpoint, with fixed effects for treatment and stratum and a random subject effect.

To examine the effect of the corrective action, we will group the strata into two sets: {A1}, for the pre-corrective-action subjects at site A, and {A2+B+C} for all post-corrective-action subjects at site A, combined with all subjects at B or C. We will test for significance of the corrective action by creating a 1 degree of freedom contrast for "treatment by corrective action", using treatment (1 df) and the two corrective action sets (1 df), and test whether the contrast is significantly different from 0, using a two-sided alpha of 0.15.

- If the contrast is not significant, then the results will be analyzed as planned, pooling across all strata pre- and post- corrective action.
- If the contrast is significant then we will carry out the analyses separately for A1 and for the combined {A2+B+C}.

We will also directly compare outcomes between A1 and A2 by calculating the LSM for the difference between the two, along with the associated 95% CI.

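### SAP 5.7.2 fits the TBUT model by ML for a reason that does not apply to the coefficient test it codes; the standard error is slightly too small for the pooled set and more clearly so for A1 alone (minor).

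*SAP*

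**What the plan says.** SAP 4.1.1 names the test that decides success: it comes from a linear mixed-effect model for the arm difference in TBUT change. The first success condition is "Two-sided p-value < 0.05"; the second is that the difference favours the study arm. Neither the SAP nor the protocol says whether that p-value is a Wald z, a Wald t or a likelihood-ratio test.

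The mixed model is written out only in SAP 5.7.2, with treatment, baseline TBUT and a random subject intercept. Its SAS code begins "Proc Mixed data=IPLdat method=ml; class SUBJ TRT", asks for the coefficient table, and sets no denominator degrees-of-freedom option. The R call ends "REML=FALSE, data=IPLdat". The choice of ML is explained in one sentence: "Note that since we are interested in testing the fixed effects, ML (maximum likelihood) versus REML (residual maximum likelihood) estimates are being used".

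SAP 5.7.1 adds a test of the treatment-by-corrective-action contrast at two-sided 0.15. If it is significant, "then we will carry out the analyses separately for A1 and for the combined" remaining strata. No other model code is given for those analyses.

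**The concern.** ML estimates the variance components as if the fixed effects were known. REML allows for having estimated them. ML variances, and the standard error of the treatment effect built on them, are therefore biased down. The confidence interval is too narrow and the p-value too small, always in the direction that favours declaring a difference. The bias grows as the number of subjects falls, so the small A1 stratum is the most exposed.

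Interest in the fixed effects is a sound reason for ML in one setting: REML likelihoods cannot be compared between models with different fixed effects, so a likelihood-ratio test needs ML. SAP 5.7.2 specifies no such comparison. At stake are the stated 5% level of the success rule and the coverage of its interval.

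A second gap goes with the first. The SAS call prints a t test with default degrees of freedom, while the lme4 call as written prints no p-value. The two are offered as alternatives, so the decisive p-value is not uniquely defined.

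**Working it through.** **Inputs from the documents.** SD of change 5 s in each arm, difference 5 − 1 = 4 s, 1:1 allocation (SAP 5.3.1). Eye correlation 0.5 and 8 wrongly treated IPL subjects at site A (SAP 5.3.2). Final size 83 subjects, 166 eyes (SAP synopsis). Two-sided 0.05 (SAP 4.1.1).

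**Assumptions.** The number of sham subjects in A1 is not given; 8 is assumed, with a range of 6 to 10. With A1 = 16, {A2+B+C} has 83 − 16 = 67 subjects. Baseline TBUT is taken as mean 4, SD 1.8, between-eye correlation 0.6.

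**The plan's own figure.** SAP 5.3.1 states "an alpha level of 0.05 and a power of 80%, the total sample size is 50 completed study eyes". Per arm, n = 2(1.960 + 0.842)² × 25/16 = 24.5, so 25 per arm and 50 in total. Power is 0.807 by normal approximation and 0.791 by exact t. Simulating the adjusted 68 subjects, with 8 IPL subjects at the control mean, gives power 0.798. Both sizes reproduce, and neither depends on the present point.

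**Closed form without baseline TBUT.** With two eyes per subject the treatment test rests on n subject means and p = 2 between-subject parameters. Then SE(ML)/SE(REML) = √((n − 2)/n).
- n = 83: √(81/83) = 0.988
- n = 16: √(14/16) = 0.935

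Putting p = 3 in the same formula would give √(80/83) = 0.982 and √(13/16) = 0.901. That charges the whole of an eye-level covariate to the between-subject stratum and overstates the shortfall. The model with baseline TBUT was therefore simulated.

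**Simulation of the 5.7.2 model under the null.** There were 40,000 trials per setting. Simulation error near 5% is √(0.05 × 0.95/40,000) = 0.11 points. The t columns use the SAS default degrees of freedom (166 − 84 = 82 at n = 83).

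| Set | SE ratio ML/REML | ML, t | ML, likelihood ratio | ML, z | REML, t |
|---|---|---|---|---|---|
| 83 subjects (42+41) | 0.984 | 5.3% | 5.4% | 5.7% | 5.0% |
| 67 subjects | 0.981 | 5.7% | 5.8% | 6.1% | 5.3% |
| A1, 8+8 | 0.917 | 7.2% | 7.7% | 9.4% | 5.2% |
| A1, 8 IPL with 6–10 sham | 0.905–0.926 | 7.1–7.5% | 7.7–8.2% | 9.2–10.2% | – |

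A separate run of 6,000 trials per setting gave ratio 0.984 with 5.4% (t) and 5.7% (z) at 83 subjects. At 8+8 it gave ratio 0.918 with 6.5% (t) and 8.9% (z). The direction is the same at eye correlations 0.3 and 0.8.

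**Splitting the causes.** REML with a z reference gives 5.3% at 83 subjects and 7.1% at 8+8. So in A1 about 7.1 − 5.0 = 2.1 of the 9.4 − 5.0 = 4.4 excess points under z come from the missing degrees-of-freedom rule and not from ML. REML with t on n − 3 df gives 5.0% and 4.9%.

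**When the pooled verdict would change.** With ratio 0.984 and t on 82 df (critical value 1.989), ML crosses 0.05 when the REML statistic is 1.989 × 0.984 = 1.957, a REML p-value of about 0.054. Only REML p-values between 0.050 and about 0.054 change sides.

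**The case against.** The strongest reply is that the test is unnamed. If the sponsor means a likelihood-ratio test, ML is required and the SAP's reason is correct; since the lme4 call prints no p-value, that is a natural reading of the R route. This stands as far as it goes. But no such comparison is specified, the SAS code prints a coefficient test, and the likelihood-ratio test under ML also exceeds 5% (5.4% at 83 subjects, 7.7% at 8+8).

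The second reply is that the effect on the pooled decision is trivial. This largely stands. Under the SAP's assumptions the chance of success at 83 subjects moves from 98.6% with REML to 98.7% with ML. If 8 of 42 IPL subjects do not respond, it moves from 92.0% to 92.5%.

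A reader might infer more than the documents support:
- **That the A1 analysis is invalid and puts the success claim at risk.** SAP 5.7.1 does not say that A1 alone decides success, and the size of A1 is assumed. At 12+12 the ML t test has 6.4%. SAP 3.3 also bases the primary analysis on a per-protocol set, from which some wrongly treated A1 subjects may be absent.
- **That the SAS default of 82 df, against about 80 available between subjects, matters.** It moves type I error from 5.00% to 5.01%.
- **That the model in 5.7.2 is certainly the decisive one.** SAP 5.7 describes the baseline-adjusted ANCOVA as additional to the primary analysis, while 5.7.2 puts baseline TBUT in the written model. The bias remains either way; without the covariate the ratio is 0.988 at n = 83.

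**Conclusion.** The point holds and is minor. ML is specified in both code lines for a reason that does not fit the coefficient test printed by the SAS code, and it makes the standard error too small.

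- **Pooled 83 subjects:** standard error about 1.6% too small; true type I error about 5.3–5.4% with a t or likelihood-ratio test and 5.7% with z. The conclusion changes only for a p-value very near 0.05.
- **A1 alone:** standard error about 7–10% too small; type I error about 6.5–7.5% with t and 9–10% with z, part of the z excess being due to the missing degrees-of-freedom rule. This is material for reading an A1 p-value or interval, but it is not shown to affect the success decision.

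The sizes rest on the SAP's SD and eye correlation, the assumed sham count in A1 and the assumed baseline TBUT distribution. The direction depends on none of these.

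**What to change.** In SAP 5.7.2:
- Replace `method=ml` by `method=reml` and `REML=FALSE` by `REML=TRUE`, and delete the sentence that justifies ML.
- State that the decisive p-value is the two-sided t test of the treatment coefficient, with a named degrees-of-freedom method. Kenward-Roger is one choice; the SAS default with REML is also adequate (5.0% at 83 subjects, 5.2% at 8+8).
- Name one program as the source of that p-value.
- Say whether the decisive model includes baseline TBUT.
- Use the same fit for the stratified and split analyses of 5.7.1.

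The cost is two code options and a few sentences, with no new data and no change in sample size. The p-value becomes slightly less favourable, and Kenward-Roger in R needs a package beyond lme4.
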